11.4 Secondary Analyses

11.4.1 Sample Size Considerations

For secondary objectives, we wish to detect differences of 20% in success and stabilization rates between subgroups, e.g., differences between patients for whom extraction was recommended and those for whom it was not. In general, we will need 110 patients for each group that is being compared (assuming 80% power, 5% significance level, and an ICC of 5%). For example, for the assessment of success between extraction and non-extraction cases, we need 110 patients treated with each technique. For the comparison of the four treatment modalities, we need 110 patients treated with each of the 4 techniques, or 440 patients total. If we recruit 840 patients at baseline, we should have adequate power for most secondary objectives, even allowing for attrition.

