11.4.2 Proposed Secondary Analyses

Analysis plan for Secondary Objectives:

Secondary objective #1a will examine how dentofacial, as well as patient and practitioner characteristics influence treatment recommendations suggested by the orthodontists. The association of each of the dentofacial, patient and practitioner characteristics specified below with different treatment recommendations will be ascertained using a chi-square test for categorical variables and either t-test or Wilcoxon rank-sum test (nonparametric equivalent). Dentofacial characteristics: profile, molar classification, maxillary crowding, mandibular crowding, posterior cross-bite, facial pattern. Patient characteristics: age, sex, race/ethnicity, insurance, education, treatment goals. Practitioner characteristics: age, sex, race/ethnicity, year received orthodontic training. For each domain of the three domains, namely, dentofacial, patient and practitioner characteristics, characteristics with $p < 0.2$ will be entered in the model, retained if $p < 0.1$. Final Generalized Estimating Equations (GEE) regression model (adjust for clustering within practice) will start with those $p < 0.1$ for each domain, and retained if $p < 0.05$ for final analysis ascertaining how dentofacial, as well as patient and practitioner characteristics influence treatment recommendations (extraction, then surgical component, fixed appliances, removable aligners, TADs).

Secondary objective #1b will examine how dentofacial, as well as patient, practitioner, characteristics influence whether or not treatment recommendations suggested by the orthodontists are accepted by the patients. Method described above will be repeated for acceptance of recommendations. Separate analyses, i.e., stratum specific, will be performed for recommendations involving extraction and those not. Of interest (though not a primary objective or specific hypothesis to be tested) within this secondary objective is exploring what factors influence whether or not patients accept treatment recommendations involving an extraction or surgical component.

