Secondary objective #2a will identify how treatment modalities, as well as dentofacial, patient and practitioner characteristics, are associated with treatment success. Success is defined above, first as positive overbite, then as amount of millimetric improvement, even if AOB is not completely closed as described in analysis for primary objective #1 above. Separate analyses, i.e., stratum specific, will be performed for treatment involving extraction and those not. The association of treatment modalities used will be assessed with whether or not treatment was successful using chi-square. The dentofacial, patient and practitioner characteristics described above, and the process to ascertain their influence on treatment recommendations, will be used to determine their association with treatment success. The process, being domain specific, will model criteria entry if $p < 0.2$; retain at $p < 0.1$. Final model, all domains combined, entry if $p < 0.1$; retained if $p < 0.05$. For this secondary objective (2a), treatment modalities will be included, first as a domain in the same manner that dentofacial, patient, and practitioner characteristics are. Then, stratum specific analyses will be performed separately according to whether or not there was an extraction.

Secondary objective #2b will identify how treatment modalities, as well as dentofacial, patient and practitioner characteristics, are associated with patient satisfaction. The above process will be repeated except the “outcome” will be patient satisfaction instead of treatment success. Separate models will be developed for overall or general

satisfaction, and for satisfaction with esthetics and with function. For this objective, whether or not treatment was successful, will be analyzed as an independent variable. A high association is expected, namely, more patients will be satisfied when treatment is successful than when not; however, it will not be a 100% (perfect) association. Some patients who are treated successfully will not be satisfied, and in contrast, some patients who are not treated successfully will be satisfied. Quantification of these proportions is of interest, as well as identifying characteristics (treatment modalities, dentofacial, patient and practitioner) that are associated with satisfaction (or dissatisfaction).

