Secondary objective #3a will examine how retainer regimens, as well as treatment modalities, dentofacial, patient and practitioner characteristics are associated with treatment stability. Stability is defined above, namely, at one year after end of active treatment there is positive overbite. First, the association of retainer regimens, namely, type of retainer (Hawley, Essix, bonded) and frequency of use prescribed (full or part-time) with treatment stability will be assessed with chi-square test. The treatment modalities (extraction, then surgery, fixed appliances, removable aligners, or TADs), dentofacial, patient and practitioner characteristics described above, will be used to ascertain their association with treatment stability. The process, being domain specific, will model criteria entry if $p < 0.2$; retain at $p < 0.1$. Final model, all domains combined, entry if $p < 0.1$; retained if $p < 0.05$. For this secondary objective (3a), retainer regimens will be included, first as a domain in the same manner that treatment modalities, dentofacial, patient, and practitioner characteristics are. Then, stratum specific analyses will be performed separately according to whether or not treatment included extraction and whether or not treatment was successful (AOB closed at end of active treatment).

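### In objectives 2a and 3a, separate p-value-selected analyses by extraction cannot show whether effects differ between extraction and non-extraction patients, and the plan gives no comparison that can

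*Protocol*

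**What the plan says.** Protocol 11.4.2 sets a selection procedure for 2a and 3a. Within each domain, factors enter at p<0.2 and stay at p<0.1. Across domains they enter the final model at p<0.1 and stay at p<0.05. The GEE model adjusting for clustering within practice is described under 1a.

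Stratified analyses follow:
- **2a (success):** "Then, stratum specific analyses will be performed separately according to whether or not there was an extraction".
- **3a (stability):** "stratum specific analyses will be performed separately according to whether or not treatment included extraction and whether or not treatment was successful".
- **1b (acceptance of recommendations):** "Separate analyses, i.e., stratum specific, will be performed for recommendations involving extraction and those not".

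Section 11.4.2 contains no interaction term, test of heterogeneity or other between-stratum comparison of estimates.

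Section 11.4.1 gives the only sizing for secondary objectives: "we wish to detect differences of 20% in success and stabilization rates between subgroups", with 110 patients per compared group at 80% power, 5% significance and an ICC of 5%. That sizes extraction against non-extraction. Nothing is sized for analyses inside a stratum.

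**The concern.** The procedure yields lists of factors that passed a threshold. When it is followed by separate analyses in extraction and non-extraction patients, the obvious way to read the strata together is to see which factors appear on one list and not the other. Whether a factor passes p<0.05 depends on stratum size as much as on its effect, so an identical effect can pass in the larger stratum and fail in the smaller.

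The protocol's background (2.1) treats extraction versus non-extraction stability as an open clinical question, and the study is meant to inform practitioners. A statement that a modality or retainer matters only in non-extraction cases would be taken as guidance, yet could come from unequal stratum sizes alone.

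**Working it through.** **Inputs.** 840 enrolled, 10% attrition to end of treatment and 20% to one year, 70% success, ICC 5% and 3 patients per practitioner (11.2). A 20-point target and 110 per group (11.4.1).

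Assumed: two-sided 5% test, rates of 50% vs 70% (or 50% vs 65%), a factor that splits each stratum evenly, and the same rates in both strata. The extraction share is not given, so it is varied.

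**The plan's own figure.** The design effect is 1 + (3−1)×0.05 = 1.10, or 1.15 at 4 per practitioner. The pooled two-proportion formula gives:
- 40% vs 60%: 97 per group; 97×1.10 = 106.7 and 97×1.15 = 111.5.
- 50% vs 70%: 93 per group; 93×1.15 = 106.9.

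The stated 110 is reproduced.

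**Evaluable patients.** Success: 840×0.90 = 756. Stability among patients closed at end of treatment: 840×0.90×0.80×0.70 ≈ 423.

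**Power in a stratum.** With share s, the effective number per factor level is m = N·s/(2×1.10). With p̄ the mean of the two rates,

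power = Φ{[d − 1.96√(2p̄(1−p̄)/m)] / √([p1(1−p1)+p2(1−p2)]/m)}.

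Example, 2a at 50:50 and 20 points: m = 378/2.2 = 171.8. The two standard errors are √(0.48/171.8) = 0.0529 and √(0.46/171.8) = 0.0517. Then (0.2 − 1.96×0.0529)/0.0517 ≈ 1.86, so power = 0.969.

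**Significant in exactly one stratum** = P1(1−P2) + P2(1−P1). In the example, 2×0.969×0.031 = 6%.

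| Objective, N | Effect | Extraction share | Power (extraction / non-extraction) | Exactly one |
|---|---|---|---|---|
| 2a, 756 | 20 points | 50% | 0.969 / 0.969 | 6% |
| | | 30% | 0.839 / 0.995 | 16% |
| | | 20% | 0.671 / 0.998 | 33% |
| | | 110 patients | 0.533 / 0.999 | 47% |
| 2a, 756 | 15 points | 50% | 0.806 / 0.806 | 31% |
| | | 30% | 0.588 / 0.917 | 43% |
| | | 20% | 0.427 / 0.947 | 57% |
| 3a closed, 423 | 20 points | 50% | 0.813 / 0.813 | 30% |
| | | 30% | 0.594 / 0.922 | 42% |
| | | 20% | 0.431 / 0.951 | 56% |

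A factor with no effect in either stratum is significant in exactly one with probability 2×0.05×0.95 = 9.5%.

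**With a direct test.** In simulation with identical effects in both strata, a test of the difference between the stratum effects rejected in 5.0% to 5.7% of runs.

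**Cost in power.** The variance of a difference of differences, with n per cell, is 2×(0.25+0.21)/n = 0.92/n. For a 20-point interaction at 80% power, n = 0.92×(1.96+0.8416)²/0.04 = 180.5. Times 1.10 this is 198.6 per cell, or about 794 in four balanced cells. That exceeds both 756 and 423.

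**The case against.** The strongest reply is that the protocol never says it will claim a difference between strata. Its objectives ask which factors are associated with an outcome, and stratum-specific models answer that within each stratum. GEE models also give estimates and confidence intervals. Interaction terms and rules for reading subgroups are often left to the SAP, which is not shown. This stands in part: no formal claim of difference is announced, and re-running the selection in each stratum is the natural reading but is not stated outright. What remains is that the protocol itself fixes p-value selection followed by separate analyses. That method cannot answer the question its strata invite, and a better one costs little.

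Four stronger readings are tempting and not supported:
- **Discordance of 50% to 61% whatever the effect.** Those values follow if whole-sample power is 80% (splits from 50:50 to 20:80). The protocol's premise differs: at its 20-point target with 756 patients, whole-sample power is above 99.9%.
- **The closed/not-closed split in 3a is equally faulty.** It is not. Section 11.3 defines stability among successfully treated patients, so the closed stratum is needed. In patients not closed, positive overlap at one year means later closure. A pooled closure interaction would mix two outcomes.
- **Nothing is labelled exploratory.** Under 1b, the protocol describes acceptance of extraction or surgical recommendations as something to explore and not a hypothesis to test. The extraction strata in 2a and 3a have no such wording.
- **Discordance is a false-positive rate.** It becomes an error only if someone reads it as a difference, so setting it directly against 5% is not like for like.

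**Conclusion.** The point holds for the extraction strata in 2a and 3a: the plan produces retained-factor lists by stratum and gives no means of judging whether effects differ. The size depends on two things the protocol does not fix, the extraction share and the true effect. At the 20-point target in 2a the chance of a misleading contrast is small with balanced strata (6%). It reaches a third at 20:80 and nearly a half if extraction only reaches 110. For 15 points it is 31% to 57%. In 3a among closed patients it is already 30% at 50:50 for 20 points, because fewer patients remain.

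These figures assume an evenly split factor, a design effect of 1.10 and single tests without the earlier screening steps. The matter concerns interpretation of secondary analyses. The primary proportions and their confidence intervals are not touched.

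**What to change.** In 11.4.2:
- **2a:** judge differences by extraction from modality-by-extraction terms in one GEE model.
- **3a:** do the same with retainer-regimen-by-extraction terms, among patients closed at end of treatment.
- **Both:** show stratum estimates with 95% confidence intervals for one fixed factor set, the same in both strata and not re-selected within stratum. Label them exploratory, and state that significance in one stratum only is not evidence of a difference.
- **1b:** apply only the same-factor-set and interpretation rules; no interaction term is needed.
- **3a closure split:** keep it as it is.

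The cost is wording and a few model terms, with no new data or visits. The downside is low power: a 20-point interaction needs about 794 patients even with balanced cells, so few differences will be claimed. The intervals will show that uncertainty, which two retained-factor lists hide.

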3 OBJECTIVES

3.1 Study Objectives

Primary: The primary objective is to estimate the proportion of patients 1) treated successfully (determined at end of active treatment), and 2) whose treatment is stable (determined at one year post active treatment).

Secondary: The secondary objectives are to:

1. Identify how dentofacial characteristics, as well as patient and practitioner characteristics, influence:
 - a. Treatment recommendations, and
 - b. Acceptance of treatment recommendations by the patient.
2. Identify how treatment modalities, as well as dentofacial, patient, and practitioner characteristics, are associated with the following, both determined at the time orthodontic appliances are removed (end of active treatment):
 - a. Treatment success, and
 - b. Patient satisfaction.
3. Identify how retainer regimens, as well as treatment modalities, dentofacial, patient and practitioner characteristics are associated with the following, both determined one year after end of active treatment:
 - a. Treatment stability, and
 - b. Patient satisfaction.

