Secondary objective #3b will examine how retainer regimens, as well as treatment modalities, dentofacial, patient and practitioner characteristics are associated with patient satisfaction, assessed one year after end of active treatment. The above process will be repeated except the “outcome” will be patient satisfaction at one year after end of active treatment instead of treatment stability. Separate models will be developed for overall or general satisfaction, and for satisfaction with esthetics and with function; all ascertained at one year after end of active treatment. For this objective, whether or not treatment was stable will be analyzed as an independent variable. A high association is expected, namely, more patients will be satisfied when treatment is successful than when not; however, it will not be a 100% (perfect) association. Some patients who are treated successfully will not be satisfied, and in contrast, some patients who are not treated successfully will be satisfied. Quantification of these proportions is of interest, as well as identifying characteristics (treatment modalities, dentofacial, patient and practitioner) that are associated with satisfaction (or dissatisfaction).

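### The satisfaction models for objectives 2b and 3b can condition on success or stability, which lie downstream of modality, and no combined model without them is specified

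*Protocol*

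**What the plan says.** Protocol Section 3.1 sets the secondary objective for the end of active treatment: "Identify how treatment modalities, as well as dentofacial, patient, and practitioner characteristics, are associated with the following", the two outcomes being treatment success and patient satisfaction. The one-year objective is parallel, with retainer regimens added to the exposures and stability in place of success.

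Section 11.4.2 describes the analyses.

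- **Objective 2a:** "Secondary objective #2a will identify how treatment modalities, as well as dentofacial, patient and practitioner characteristics, are associated with treatment success". The process is staged. For the first step, "The association of treatment modalities used will be assessed with whether or not treatment was successful using chi-square". Domain-specific models follow (entry p<0.2, retained p<0.1), with modality as one domain. Last comes a model combining all domains (entry p<0.1, retained p<0.05). The paragraph on objective 1a names GEE, to allow for clustering within practice, for the final model.
- **Objective 2b:** "Secondary objective #2b will identify how treatment modalities, as well as dentofacial, patient and practitioner characteristics, are associated with patient satisfaction". On method, "The above process will be repeated except the “outcome” will be patient satisfaction instead of treatment success". For this objective, "whether or not treatment was successful, will be analyzed as an independent variable". The plan adds: "A high association is expected, namely, more patients will be satisfied when treatment is successful than when not".
- **Objective 3b:** the process is repeated for one-year satisfaction, and "whether or not treatment was stable will be analyzed as an independent variable".

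The 2b and 3b paragraphs also state a second interest: how often successfully treated patients are dissatisfied, and the reverse.

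**The concern.** Success is determined at appliance removal and stability about a year later. Both come after the choice of modality, and stability also comes after the retainer regimen is prescribed. They are not baseline confounders. By the plan's own account they lie on a path from modality to satisfaction: 2a and 3a look for the first link, and the 2b text expects the second to be strong.

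If such a variable sits beside modality in the final model, the modality coefficient describes satisfaction among patients with the same closure result. That is a legitimate quantity, but it differs from the overall association that most readers would take from the objective. The retention rule adds to the problem. A term expected to be strongly associated will probably stay, and a modality working mainly through closure will tend to fall short of p<0.05 and leave the final model. A reader of that model could then conclude that modality has no bearing on satisfaction when patients do end up more satisfied with one modality than with another.

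**Working it through.** **The plan's own figure, for scale.** This point disputes no number in the protocol. Section 11.4.1 gives 110 patients per group to detect a 20-point difference in success or stabilization (80% power, 5% level, ICC 5%). The usual two-proportion formula (pooled variance, two-sided, no continuity correction) times a design effect of 1 + (m − 1) × 0.05 gives:

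- 45% v 65%: 96 × 1.15 (m = 4) = 110.4
- 40% v 60%: 97 × 1.10 (m = 3) = 106.7, or 97 × 1.15 (m = 4) = 111.5

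The base rates are not stated, but rates near 50% reproduce 110. The 20-point difference in success is used below.

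**Inputs that are assumptions.** The protocol gives no satisfaction rates by closure status and no direct effect of modality on satisfaction. Both are assumed here.

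**Formula.** P(satisfied | modality) = P(success | modality) × s1 + [1 − P(success | modality)] × s0, where s1 and s0 are the satisfaction rates with and without closure.

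**Illustration with no direct effect.** Success 60% v 80%, s1 = 90%, s0 = 50%:

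- Modality A: 0.6 × 0.9 + 0.4 × 0.5 = 0.74
- Modality B: 0.8 × 0.9 + 0.2 × 0.5 = 0.82
- Total difference: 8 points; OR = (0.82/0.18)/(0.74/0.26) = 1.60
- Within closed cases, 90% v 90%; within cases not closed, 50% v 50%. The success-adjusted difference is 0 and the OR is 1.00.

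**Range, still with no direct effect.** The total difference is 0.20 × (s1 − s0). With success of 50% v 70%:

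| s1 / s0 | Total satisfaction | Difference | Total OR | Adjusted OR |
|---|---|---|---|---|
| 90 / 70 | 80% v 84% | 4 points | 1.31 | 1.00 |
| 90 / 60 | 75% v 81% | 6 points | 1.42 | 1.00 |
| 90 / 50 | 70% v 78% | 8 points | 1.52 | 1.00 |
| 95 / 30 | 62.5% v 75.5% | 13 points | 1.85 | 1.00 |

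**With a direct effect.** Success 50% v 70%, s1 = 90%, s0 = 50%, and a direct effect of ±0.5 on the log-odds scale:

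- Adjusted OR 1.65: total difference 14.3 points, total OR 2.29. The effect survives adjustment, though reduced.
- Adjusted OR 0.61: total difference 0.5 points, total OR 1.02. The model with success shows a modality as unfavourable although overall satisfaction is practically equal.

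**Chance of p<0.05 for modality.** This uses the 60% v 80% illustration, with simulated logistic fits and independent patients. Without v with success in the model, the chance is about 29% v 5% at 110 per group, 58% v 5% at 250, and 74% v 6% at 378. The figures with success in the model are simply the type I error, because the direct effect was set to zero. The simulation tests one coefficient. It includes neither practice clustering nor the staged selection.

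**The case against.** The strongest reply is that the plan is not a single model. Repeating the 2a process gives a chi-square of modality against satisfaction, and apparently a modality domain model, before anything is adjusted for success. In the illustration, 74% v 82% would be visible in the first table. Nor does the text say that success is forced into every model. Both points stand. They do not settle the matter, because the chi-square is also unadjusted for confounders and practice clustering, and no combined GEE model without success or stability is specified.

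A reader might infer that the planned models fail to answer the objective. The documents do not support that. The objective is worded as association, and an association given closure is still an association. It also fits the stated interest in patients whose satisfaction and success diverge, and Section 3.2 lists end-of-treatment success as a factor of interest for the one-year outcomes. What is missing is a statement of which association each model targets.

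A reader might also infer that the modality association vanishes under adjustment. That follows only from assuming no direct effect. Section 2.1 says that many patients favour aligners for esthetics and comfort, and that TADs and surgery differ in invasiveness and cost. Such effects could be direct. For 3b, the main measure in Section 3.2 is satisfaction with retainers, and nothing shows that it works mainly through overbite stability.

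Finally, at 110 per group even the model without success detects the illustrated effect only about 29% of the time. At that size, adjustment is not the main reason for a missed finding.

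**Conclusion.** The point holds as a matter of what the final models can conclude. A combined satisfaction model containing success (2b) or stability (3b) conditions on a variable that the plan itself treats as downstream of modality, and of retainer regimen in 3b. It estimates the association beyond closure, and the p<0.05 rule can remove a modality whose association runs mainly through closure.

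For 2b, with a 20-point difference in success and assumed satisfaction gaps of 20 to 65 points between closed and unclosed cases, the part removed is 4 to 13 points when there is no direct effect. With a direct effect, part of the association remains, and the two models can lead to different conclusions. For 3b the mechanism is the same, but its size is not established. All satisfaction rates and direct effects used here are assumptions.

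The objectives are secondary and the primary estimates are untouched. It is worth correcting because the protocol has already chosen the covariate and the change is cheap.

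**What to change.** In Section 11.4.2, for each satisfaction outcome in 2b and 3b:

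1. Prespecify the combined, clustered (GEE), covariate-adjusted model **without** success or stability, and name it as the main answer on modality associations and, in 3b, retainer associations.
2. Add success (2b) or stability (3b) in a second, labelled model. Use it to quantify that variable's link with satisfaction and the association that remains given closure.
3. State in one sentence which association each model targets.

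This keeps both stated aims and uses data already collected. The cost is one extra model per satisfaction outcome and a longer results table.
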